#### CONFIDENTIAL AND PROPRIETARY

**Clinical Protocol - Device** 

Study Number: Journey II CR.2020.11

A Prospective Multi-Centre Study in Patients Undergoing Total Knee Replacement Version: 2.0, 02Jun2021 with JOURNEY II CR Total Knee System

Page: 8 of 57

1. All the data will be collected based on knee, except inform consent, inclusion/exclusion and demographic/medical history.

- Patient reported outcome can be assessed and collected remotely for follow-up period.
- The radiographic images prior to 3 months can be accepted for pre-operative screening data due to hospital's SoC.
- Radiographic assessment can be conducted at discharge if it's the SoC of the site.
- Radiographic images can be retrieved from other hospital/facility under specific image acquisition protocol and send back to site for assessment.
- Exit form to be completed at the point of withdrawal if the study is not completed.

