## 7.7 Lost to Follow-up

A subject will be considered lost to follow-up if he/she does not appear for the scheduled study visit for 2 consecutive visits, and study personnel are unable to contact the subject.

Some actively enrolled subjects will not return for follow-up exams on time. Study personnel must make a reasonable effort to contact the subject and document the following contact attempts before declaring a subject to be lost to follow-up: the subject has been contacted according to the site's policies, but no fewer than two documented phone contacts and one certified letter without response. Copies of all attempts to reach the subjects by mail or email and/or the attempts to contact the subject via other means should be documented, and that documentation should be kept with the subject's source documents.

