## 7.8.2 Withdrawal from Study

The Investigator may withdraw subjects from the study for many reasons, including but not limited to the following:

Study Number: Journey II CR.2020.11

- Subject noncompliance (e.g., did not follow instructions)
- Subject lost to follow-up
- The Investigator or the Sponsor stops the study for any reason and decides to withdraw subject(s) from the study
- Concurrent illness
- Adverse Events/Adverse Device Effects
- Any other significant reason identified by the Investigator

For each case, information will be obtained in the source document and the Case Report Form (CRF), detailing circumstances leading to the withdrawal.

Subjects who drop out or are withdrawn will not be re-entered into the study at a later date.

If at any point during the study, the prosthesis needs to be revised for any reason the following will apply: Subjects shall continue to have follow-up visits in order to monitor the subject's health status. Potential data following the revision surgery will not be included as study data but presented separately as safety data.

For minor revisions, where not the whole knee implant system is replaced (e.g. replacement of inserts) the subject shall continue with the study specific schedule and data will be presented.

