## 9.1.11 Discontinued Subjects

Discontinued subjects are those who voluntarily discontinue participation, who are withdrawn for reasons of safety or use of prohibited concomitant medication/therapies, who are lost to follow-up, refer to section 7.8 for further details. Where possible, a full Exit Visit should be completed for all subjects who discontinue the study early. Where consent is withdrawn, the date and any reason given for discontinuation should be captured, at a minimum (see Section 7.8.3).

Finally, if appropriate, the Investigator will also advise the subject of subsequent therapy and/or procedures necessary for their medical condition.

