7.4 Derived Data

Time to Revision:

Time to revision (in months) = (Revision Date - Operative Date)/30.4375.

2011 Knee Society Score (KSS)

The 2011 KSS consists of 34 questions and provides sub-scores across 5 dimensions as shown in Table 4.

Table 4 2011 Knee Society Score

#	Sub-Score	# Questions	Range	Completion by
1	Objective Knee Score	7	0-over 100	Surgeon
2	Subject Satisfaction Score	5	0-40	Subject
3	Subject Expectation	3	3-15	Subject
4	Functional Knee Score	19	0-100	Subject

The Knee Society Score (KSS) comprises information on Objective Knee Indicators (range 0 to over 100 points), Patient Satisfaction (range 0-40), Patient Expectation (range 0-15), and Functional Activities (range 0-100). The KSS endpoints are derived from a series of questions that relate to everyday activities. More elaborate information for deriving the KSS endpoints are described in the publication by Scuderi et al (2012) [1]. However, an abbreviated description of the KSS endpoints used in the study is described in this SAP.

- Objective Knee Score (Completed by Physician/Surgeon)
- The objective score allows for more than 100 points in patients with greater than 125° of flexion and a stable painless knee as outlined below.

CONFIDENTIAL AND PROPRIETARY

Statistical Analysis Plan

A Prospective Multi-Centre Study in Patients Undergoing Total Knee Replacement with JOURNEY II CR Total Knee System Number: Journey II

CR.2020.11 ST: ST1197

Version: V1.0, 20-MAY-

2024

Page: 11 of 20

- "Alignment" allows for a maximum of 25 points and is determined on a weight-bearing AP radiograph measuring the femoral-tibial (Anatomic) axis.
- "Instability" allows for a maximum of 25 points for a knee that is stable in the coronal and saggital axis.
- "Joint Motion" allows one point for each 5° of joint motion with a potential for greater than
 25 points to be assigned for patients with greater than 125° of motion. There are deductions for flexion contracture and extension lag.
- "Instability" has a maximum allowable point allocation of 25+.

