Any revisions, and detail of, will be provided in a listing.

If feasible based on data available at premature termination, Kaplan Meier estimates and 95% confidence intervals will be provided by surgical method. Knees implanted without an on-study revision will be censored on the date of their last known follow-up visit. Any premature knee discontinuation from study due to a subject's death or for any other reason, excluding lost-to-follow-up, will be censored on the date of this discontinuation. Cumulative implant survivorship also be graphically illustrated.

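### SAP 7.11 censors early leavers other than losses to follow-up at the discontinuation date without requiring that revision status was known then, so the survivorship curve can be too favourable

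*SAP*

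**What the plan says.** SAP 7.4 defines the time scale: "Time to revision (in months) = (Revision Date - Operative Date)/30.4375". SAP 7.11, under Time to Revision, makes the curve conditional: "If feasible based on data available at premature termination, Kaplan Meier estimates and 95% confidence intervals will be provided by surgical method". It then gives two censoring rules.

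- General rule: "Knees implanted without an on-study revision will be censored on the date of their last known follow-up visit".
- Early discontinuation: knees leaving through death or "for any other reason, excluding lost-to-follow-up, will be censored on the date of this discontinuation".

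Because the second rule leaves out loss to follow-up, those knees fall back on the first. Protocol 7.7 counts a subject as lost only "if he/she does not appear for the scheduled study visit for 2 consecutive visits" and cannot be reached by study staff.

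Two protocol sections bear on what is known at discontinuation. Section 7.8.2 lists this withdrawal reason: "The Investigator or the Sponsor stops the study for any reason and decides to withdraw subject(s) from the study". Section 9.1.11 says: "Where possible, a full Exit Visit should be completed for all subjects who discontinue the study early"; when consent is withdrawn, the minimum is a date and any reason offered. A footnote to the study schedule adds: "Exit form to be completed at the point of withdrawal if the study is not completed".

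SAP 7.10 records that the study had already been terminated when the SAP was written.

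**The concern.** The two rules give different dates for the same unrevised knee, and the later date is not tied to knowledge of the implant. A discontinuation date can be entered without an examination or a conversation: an exit form is a record, an exit visit is not guaranteed, and consent withdrawal needs only a date. If the last real information came from a visit months before, the interval in between counts as time at risk, although a revision in it may never have reached the site. That lowers the estimated revision rate and inflates the late numbers at risk. The confidence interval does not show the error.

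The exception for loss to follow-up shows that the authors accept the principle that unknown status should not earn follow-up time. It is narrow, though. Visits are 12 months apart after year 1, so a subject who missed only the last visit before closure does not meet the two-visit definition and, if then discontinued, is credited up to the discontinuation date.

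**Working it through.** The documents give no revision rate, termination date or interval from last visit to exit, so there is no figure in the plan to reproduce. The check asks how large the bias could be.

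**Inputs from the documents.** Visits at 6 weeks, 6 months and 1, 2 and 3 years; 18 months of enrolment (Protocol 8.1). From the visit windows, the longest interval between the 1-year and 2-year visits with none missed is (730 + 60) − (365 − 30) = 790 − 335 = 455 days.

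**Assumptions.** Uniform enrolment; one termination date, 2.5 or 3.0 years after first enrolment; constant revision hazard λ of 0.5%, 1% or 2% per year. The curve is read at 1.9 years, just before the 2-year visit.

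**Unconfirmed time.** Under these assumptions the mean interval from last scheduled visit to termination is about 5 months (24% of follow-up time) for termination at 2.5 years and 7 months (26%) for 3.0 years. This is the most that could be credited without confirmation.

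**Size of the bias if no knee is contacted at exit and all revisions in the gap are missed.** True survival at 1.9 years is exp(−1.9λ). Up to year 1 nothing is lost, because every knee reaches its 1-year visit. Between 1 and 1.9 years, only knees followed to at least 2 years can show a revision, but all knees not yet terminated stay in the denominator.

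- Termination at 2.5 years (follow-up uniform on 1.0 to 2.5 years): the apparent hazard at time t is λ × 0.5/(2.5 − t). Over 1 to 1.9 it integrates to λ × 0.5 × ln(1.5/0.6) = 0.458λ instead of 0.9λ. Apparent survival is exp(−1.458λ).
- Termination at 3.0 years (follow-up uniform on 1.5 to 3.0 years): from 1 to 1.5, λ × (1/1.5) × 0.5 = 0.333λ; from 1.5 to 1.9, λ × ln(1.5/1.1) = 0.310λ. Apparent survival is exp(−1.643λ).

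A large simulation of the same set-up agrees with these formulas to within 0.01 points. It gives, for survivorship at 1.9 years (%):

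| λ per year | Truth | SAP rule, status known at exit (2.5 y / 3.0 y) | SAP rule, gap revisions all missed (2.5 y / 3.0 y) | Overstatement, points |
|---|---|---|---|---|
| 0.5% | 99.05 | 99.07 / 99.06 | 99.28 / 99.18 | 0.23 / 0.13 |
| 1% | 98.12 | 98.12 / 98.12 | 98.56 / 98.37 | 0.44 / 0.25 |
| 2% | 96.27 | 96.27 / 96.26 | 97.14 / 96.76 | 0.87 / 0.49 |

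At λ = 1%, a true revision risk of 1.88% is reported as 1.44% or 1.63%, which is 23% or 13% too low in relative terms. At about 1 year the bias is essentially nil. For scale, the binomial 95% half-width for a full cohort of 240 knees is 1.96 × √(0.98 × 0.02/240) = 1.8 points at 98% survival and 2.5 points at 96%.

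**Does moving the date back cure it?** Only if revised and unrevised knees are treated alike. Censoring at the last visit and leaving out gap revisions returns the truth (98.14% and 98.12% at λ = 1%). Censoring unrevised knees at the last visit while counting every gap revision understates survivorship by about 0.2 to 1.9 points (for example 97.16% against 98.12%).

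A mixed case (termination at 2.5 years, λ = 1%, half the knees uncontacted, half of their gap revisions reported spontaneously) has a true revision risk of 1.88%. The estimates are about 1.76% under the SAP rule, 2.02% with last-confirmed-status censoring and all known revisions counted, and 1.87% with spontaneous late reports also left out.

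**The case against.** The strongest reply is that the protocol does provide for contact and event capture. An exit form accompanies each withdrawal, a full exit visit is expected where feasible, and adverse events of every kind are recorded with their dates (Protocol 12.3). A site may also learn of a revision by performing it. If status is known at discontinuation, the SAP rule is the usual unbiased one, and censoring at the date of death is a common convention. This stands, and it is why the bias is conditional.

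A reader might infer that the rule credits time nobody observed, that it covers nearly every unfinished knee, and that survivorship is therefore overstated. The documents support none of the three as fact. They do not say how many exits lacked contact. They also do not say whether closure of the study counts as early discontinuation of a knee: Protocol 7.8.2 makes that reading possible, but the general rule could equally be taken to cover knees still under follow-up at closure. That silence is itself a gap, since two programmers could draw two different curves.

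Materiality is also limited. The curve is produced only if feasible, SAP 7.15 confines the analysis to description, all revisions are listed, and SAP 7.6 tabulates expected and actual follow-up by visit. The largest bias computed is below the sampling half-width. But that bias is systematic and, under the SAP rule, can only favour the device.

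Finally, a careless correction can do more harm than the rule it replaces, as the last calculation shows. The fix has to address this.

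**Conclusion.** The point holds as a defect of specification with a possible bias, not as a demonstrated one. SAP 7.11 sets a censoring date that need not be a date of known implant status, does not say how termination by the sponsor is handled, and leaves two rules that conflict for the same knee. Survivorship can be overstated by anything from zero (status confirmed at exit, or all gap revisions captured) to about 0.1 to 0.9 percentage points at about 2 years (no contact at exit and all gap revisions missed). That range rests on the assumed revision rates, termination times, uniform enrolment and constant hazard. The text of the rule is certain; the bias actually realised cannot be judged from the documents. It is worth correcting because the curve is the implant survivorship summary and the change is small.

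**What to change.** Replace the two censoring sentences in SAP 7.11 with one rule, for example:

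> Every unrevised knee is censored at the last date on which implant status was confirmed (study visit, exit visit, documented remote contact, or death with the implant confirmed unrevised), whatever the reason for leaving, including termination of the study by the sponsor. A revision learned of only through a spontaneous report after a knee's last confirmed contact is listed but not counted as an event in the main Kaplan-Meier estimate.

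The second sentence ensures that revised and unrevised knees are ascertained alike. Show the discontinuation-date version, with all known revisions counted, as a sensitivity analysis. If the two curves agree, exit contact was good enough for the choice not to matter.

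The cost is a short change of wording, one different date variable and one extra curve. Follow-up will be slightly shorter, late confidence limits wider, and the survivorship figure possibly a little less favourable. If status was confirmed at every exit, the estimate does not change.

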7.12 Analysis of Exploratory Endpoint(s)

Not Applicable

7.13 Analysis of Safety Endpoint(s)

All safety data will be summarized overall, and by the different surgical methods (resurfaced/unresurfaced).

Adverse event table summaries will be provided using the most stringent classification from Investigator and Adverse Event Monitoring Board (AEMB). Both Investigator and AEMB classifications will be provided alongside the most stringent classification in the Listings.

The number of events and the number of subjects reporting: adverse events (AE) and serious adverse events (SAE), adverse device effects (ADE), serious adverse device (SADE) and unanticipated serious adverse device effects (USADE) will be summarised.

In addition, AEs will be summarised by: frequency, severity, anticipated/unanticipated, relationship to device and procedure; treatment and surgical intervention details (type, reason), outcome and duration of adverse events at trial discontinuation will be summarised.

CONFIDENTIAL AND PROPRIETARY

Statistical Analysis Plan

A Prospective Multi-Centre Study in Patients Undergoing Total Knee Replacement with JOURNEY II CR Total Knee System Number: Journey II

CR.2020.11 ST: ST1197

Version: V1.0, 20-MAY-

2024

Page: 20 of 20

All safety analysis will be performed using the SAF analysis population.

Device Deficiencies

The number of device deficiencies, and the number with potential to cause an SAE will be summarised.

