6.2 Randomisation

No randomization has been planned for this study. The decision on whether to resurface patella or not will be made by investigator based on patient's conditions.

CONFIDENTIAL AND PROPRIETARY

Statistical Analysis Plan

A Prospective Multi-Centre Study in Patients Undergoing Total Knee Replacement with JOURNEY II CR Total Knee System Number: Journey II

CR.2020.11 ST: ST1197

Version: V1.0, 20-MAY-

2024

Page: 8 of 20

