6.3 Interim Analysis

The protocol stated an interim analysis was planned after the 2 year visit. However due to premature termination of the study no interim analyses will be performed.

7 STATISTICAL ANALYSIS 7.1 General

Smith+Nephew's Global Biostatistics group will conduct the statistical analysis for this study. Unless otherwise stated, all significance tests and hypothesis testing will be two-sided, performed at the 5% significance level. Resulting p-values will be quoted and 95% two-sided confidence intervals will be generated where appropriate. All p-values will be rounded to three decimal places, p-values less than 0.001 will be presented as '<0.001' in all tables.

Where data summaries are specified, categorical and ordinal variables will be summarized with frequencies and percentages. Continuous variables will be summarized with the following summary statistics: number of observations, mean, median, standard deviation, minimum and maximum values. All analyses will be performed in SAS 9.4 (or later).

All table summaries will be provided overall, and by surgical method (resurfaced/un-resurfaced patella).

Example mock shells are provided below:

Table: Demographics by subject				
		Resurfaced Patella	Un-Resurfaced Patella	Overall
Age	Mean			
	Median			
	Std			
	Min			
	Max			
	Q1			
	Q3			
	Inter Quartile Range			
	N			
Age	<65			

CONFIDENTIAL AND PROPRIETARY

Statistical Analysis Plan

Number: Journey II

CR.2020.11 ST: ST1197

Version: V1.0, 20-MAY-

2024

Page: 9 of 20

A Prospective Multi-Centre Study in Patients Undergoing Total Knee Replacement with JOURNEY II CR Total Knee System

>=65		
N		

PROM by knee				
Assessment		Resurfaced Patella	Un-Resurfaced Patella	Overall
Pre-Operative	Mean			
	Median			
	Std			
	Min			
	Max			
	Q1			
	Q3			
	Inter Quartile Ran	nge		
	N			
6 Month				
1 Year				
2 Year				
3 Year				

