7.6 Disposition Data

A table will be provided summarising number of subjects.

Subject (and knee) disposition will be summarized after completion of the study using frequency (n) and percentage (%) of subjects (or knee) who completed and who did not complete the study. For those who did not complete the study, the primary reason for discontinuation will additionally be summarized.

CONFIDENTIAL AND PROPRIETARY

Statistical Analysis Plan

A Prospective Multi-Centre Study in Patients Undergoing Total Knee Replacement with JOURNEY II CR Total Knee System Number: Journey II

CR.2020.11 ST: ST1197

Version: V1.0, 20-MAY-

2024

Page: 16 of 20

The number of knees that enter the study, and the number of knees with follow up information will be provided by visit:

- Theoretically due: number enrolled and implanted with study device
- Deaths: cumulative number of subjects that died prior to the study visit
- Revisions / failures: cumulative number of subjects that revised/failed prior to the study visit
- Cumulative terminations: terminated from study other than from revision or death
- Expected = theoretical due cumulative (deaths + revisions + termination)
- Actual = actual number of subjects at follow up visit
- Follow up = actual / expected x 100.

The number of subjects that have discontinued from the study and reasons for withdrawal will be summarised.

Study duration and the duration between surgery and each visit will be summarised.

Screening and enrolment summary: For each centre/site, dates that the first subject was screened/enrolled and the last subject completed will be provided, duration (site, 1st enrolled – final subject exit), together with number of subjects enrolled and number of subjects completed 10 year visit.

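### SAP 7.13 summarises adverse events by patella cohort without time at risk, so if follow-up differs between cohorts after early termination, that difference could read as a safety difference

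*SAP*

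**What the plan says.** SAP 7.13 states that "All safety data will be summarized overall, and by the different surgical methods". The measures are numbers of events and numbers of subjects; the list starts "The number of events and the number of subjects reporting: adverse events (AE" and runs on to SAE, ADE, SADE and USADE. The section gives no person-time, incidence rate, fixed post-operative window or censoring rule for adverse events. The only duration it mentions is how long an event lasted.

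Four other places bear on this:

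- SAP 7.1 splits every summary table by surgical method and says "categorical and ordinal variables will be summarized with frequencies and percentages". Subjects with an event should therefore carry a percentage.
- SAP 7.6 says "Study duration and the duration between surgery and each visit will be summarised", and tabulates knees expected and knees seen at each visit. Under 7.1 these should also appear by cohort.
- SAP 7.11 (Time to Revision) plans that, if feasible, "Kaplan Meier estimates and 95% confidence intervals will be provided by surgical method", with censoring. Revision is the only outcome given a time-at-risk method.
- SAP 6.2 says "No randomization has been planned for this study"; whether to resurface is the investigator's choice.

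Protocol 8.1 expected entry over 18 months and 36 months of follow-up after surgery. SAP 7.10 records that the study was terminated early, and SAP 7.15 drops all testing in favour of descriptive statistics.

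**The concern.** With a full 36 months for every subject, counts and percentages would have been comparable apart from drop-out. Early termination removes that. A knee operated on early in enrolment is observed for longer than one operated on late, and nothing in the design balances surgery dates between the cohorts. Cohort could also follow site: the protocol labels the design as comparative across sites, and Protocol 4.1 notes that use of patella replacement differs by country. Sites that open earlier would then give their dominant cohort more follow-up.

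The SAP responded to termination by removing tests but left the adverse-event measures unchanged. Objective 2 asks what resurfacing does to outcomes. With testing gone, the side-by-side safety columns are the main evidence on its safety side. A gap between them might reflect only when each cohort was enrolled.

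**Working it through.** The documents give no adverse-event rate, no termination date, no enrolled numbers and no follow-up by cohort. There is therefore no plan figure to reproduce, and what follows is an illustration of size.

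**Inputs from the documents**

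- Planned entry period: 18 months (Protocol 8.1), about 548 days.
- Enrolment not before protocol version 2.0 of 02 June 2021, because Protocol 23.1.3 puts that amendment in effect before enrolment.
- SAP date: 20 May 2024, by which time the study had already been terminated (SAP 7.10).
- Planned maximum of 240 knees per cohort (Protocol 7.1).

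**Assumptions**

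- Follow-up runs to the SAP date, as a proxy for the unstated termination date.
- Enrolment is uniform, with one cohort entirely in the first nine months and the other entirely in the last nine.
- True risk is the same in both cohorts: 0.2 events per knee-year, constant. A variant adds a perioperative burst of 0.2 events per knee.
- 1 October 2021 is used as an alternative, assumed start.

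**Step 1: can follow-up still be the planned length?** From 02 June 2021 to 20 May 2024 is 1083 days, or 1083/30.4375 = 35.6 months. No knee could have reached a nominal 36 months (1095 days) by the SAP date. If the planned entry period was used in full, follow-up differs by up to 18 months between knees.

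**Step 2: mean follow-up under full separation.** The mean surgery dates of the two halves are start + 137 and start + 411 days.

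| Start | First-half cohort | Second-half cohort | Ratio |
|---|---|---|---|
| 02 June 2021 | (1083 − 137)/365.25 = 2.59 y | (1083 − 411)/365.25 = 1.84 y | 1.41 |
| 1 October 2021 (assumed) | (962 − 137)/365.25 = 2.26 y | (962 − 411)/365.25 = 1.51 y | 1.50 |

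At a constant rate the event ratio equals the follow-up ratio. With parallel enrolment it is 1.0.

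**Step 3: events and subjects.** Expected events = knees × (b + r × years), and share with an event = 1 − exp(−(b + r × years)), where r = 0.2 per year and b is the burst. Take 240 knees per cohort and the June 2021 start.

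- b = 0: 240 × 0.2 × 2.59 = 124 against 240 × 0.2 × 1.84 = 88 events, ratio 1.41. Subjects with an event: 40.4% against 30.8%. Percentages correct for cohort size but not for time.
- b = 0.2: (0.2 + 0.518)/(0.2 + 0.368) = 1.26. Subjects with an event: 51.2% against 43.4%.

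Other follow-up pairs, also assumed:

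| Follow-up | Event ratio, b = 0 | Event ratio, b = 0.2 |
|---|---|---|
| 24 vs 24 months | 1.00 | 1.00 |
| 24 vs 18 months | 1.33 | 1.20 |
| 24 vs 12 months | 2.00 | 1.50 |

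**Step 4: does one overall rate per knee-year cure it?** Only if the hazard is constant. With b = 0.2 and r = 0.2, 24 months gives (0.2 + 0.4)/2 = 30 per 100 knee-years, and 12 months gives (0.2 + 0.2)/1 = 40. At equal true risk the longer-followed cohort now looks safer, so the distortion is reversed rather than removed.

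**The case against.** The strongest reply is that nothing shows unequal follow-up. Resurfacing is decided patient by patient, and Protocol 8.5 describes continuous screening and a 1:1 ratio, so both cohorts may have accrued side by side. That stands. A reader might infer from SAP 7.13 that the cohort followed longer is bound to look less safe, or that a 41% to 50% distortion is present. The documents support neither. Those figures need complete separation of enrolment, a constant rate, the SAP date standing in for termination and, for the larger one, an assumed start date.

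It is also fair that the plan mitigates the problem in part. SAP 7.1 implies percentages. SAP 7.6, read with 7.1, should show study duration and knees seen per visit by cohort, so an imbalance would be visible. Revision, which depends heavily on length of follow-up, has a censored analysis if feasible. With no tests planned, no error rate or decision rule is affected.

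What remains is that a reader who sees different average durations in a disposition table cannot work back to risks over a common period. The SAP already accepts censoring for revision, and adverse events are exposed to the same variation in follow-up.

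**Conclusion.** SAP 7.13 takes no account of time at risk for adverse events, in a study where follow-up now varies with surgery date and may differ between non-randomised cohorts. If it does differ, the longer-followed cohort could show more events, and a higher percentage of subjects with events, at equal true risk.

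The size is unknown. The illustrations run from 1.0 with parallel enrolment to 1.41 or 1.50 under complete separation and a constant rate, and about 1.26 for the June 2021 start with the assumed burst. All rest on the assumptions listed in the working. This is a gap in how the descriptive safety results can be read, not an invalid analysis, and it is worth closing because it costs little.

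**What to change.** In SAP 7.13, keep the counts and percentages and add, by cohort, one of the following:

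- AE, SAE, ADE and SADE within fixed windows from surgery (to 6 weeks, 6 months, 1 year and 2 years), with the number of knees under observation for each window; or
- cumulative incidence of the same categories, censored at last follow-up as already planned for revision. This also handles knees whose follow-up ends inside a window.

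Show total knee-years per cohort beside the adverse-event table. If events per 100 knee-years are reported, give them by window, or add a note that a single overall rate assumes a constant hazard and can favour the longer-followed cohort when events cluster around surgery.

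The cost is one extra table built from surgery, event and last-follow-up dates already held. No new data are needed.
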